4.1.7 Handling of missing data and incomplete date

Missing safety data will generally not be imputed. However, safety assessment values of the form of “<x” (i.e. below the lower limit of quantification) or >x (i.e. above the upper limit of quantification) will be imputed as “x” in the calculation of summary statistics but displayed as “<x” or “>x” in the listings.

Additionally, adverse events that have missing causality (after data querying) will be assumed to be related to study drug, with the exception of causality assessments that are not applicable for the patient. The original incomplete or missing dates will be presented in the listings.

- Adverse events: all AEs will be considered as treatment-emergent unless the opposite can be clearly stated.
- Concomitant medications: all medications will be considered as concomitant unless the opposite can be clearly stated.

The original incomplete or missing start dates will be imputed as below:

- Missing day: impute the 1st of the month unless month is same as month of first dose of study drug then impute first dose date
- Missing day and month: impute 1st January unless year is the same as first dose date then impute first dose date

- Completely missing – impute first dose date unless the end date suggests it could have started prior to this in which case impute the 1st January of the same year as the end date.

When imputing a start date, ensure that the new imputed date is sensible i.e. is prior to the end date of the AE or study.

Partial AE or medication end dates will be imputed as follows:

- If only day is missing: impute day as the earlier of either the date of DCO or the last day of the month;
- If day and month are missing: impute day and month as the earlier of either the date of DCO or the last day of the year;
- If the end date is missing, then the analysis end date will not be imputed.

Imputed dates will not be used for deriving duration of events or treatment.

If a patient is known to have died where only a partial death date is available then the date of death will be imputed as the latest of the last date known to be alive +1 from the database and the death date using the available information provided:

- For missing day only – using the 1st of the month
- For missing day and month – using the 1st of January

If there is evidence of death but the date is entirely missing, it will be treated as missing, i.e. censored at the last known alive date.

4.2 Analysis methods

4.2.1 Disposition of patients

The summary table of disposition will include no. of patients screened and enrolled, and the distribution of disposition events. Reason for screening failure will also be presented.

Important protocol deviations recorded by clinical operation team will be summarized according to predefined categories. All protocol deviations will also be listed.

The number and proportion of patients included and excluded from SS will be summarized. For those excluded from SS, reasons for exclusion will be summarized.

The excluded patients will be identified on data review meeting. The reasons will be imported to analysis dataset from an external document.

4.2.2 Demographics and baseline characteristics

All the variables below will be summarized using descriptive statistics for continuous and categorical variable accordingly. Specific of other category in each variable will not be presented in summary tables but listed. Variables which are not presented in the following statements but collected in EDC will not be summarized but listed.

4.2.2.1 Demographics

Demographics includes age, age group (<65 years, ≥65 years), sex, race, ethnicity, height, weight and body mass index (BMI) at screening.

4.2.2.2 Pathology at screening

Variables of pathology of SCLC at screening include time from original diagnosis to the first dose of study treatment, time from the latest assessment date to the first dose of study treatment, pathology at diagnosis with primary tumor, regional lymph nodes and distant metastases TNM classification, and stage/AJCC stage.

4.2.2.3 Extent of SCLC upon entry to study

Variables of extension of disease upon entry to study include whether the patient had recurrence of earlier cancer and sites of local/metastatic disease.

4.2.2.4 Medical and surgical history

Variables to describe medical history include no. of patients with any medical history and coded terms of medical history. The terms of medical history will be coded using the latest version of MedDRA before database lock. The coded terms will be sorted according to the descending order of occurrence rate of system organ class (SOC) and preferred term (PT) within each SOC.

The event recorded in medical history page will be classified as medical history and current disease for summary. Any event that ended prior to the first dose of the study treatment will be considered as medical history. While those which ended after the first dose or are still ongoing will be considered as current disease.

Surgical history will be summarized in the same way as medical history.

4.2.2.5 Anti-cancer therapy

Number and percentage of patients had previous cancer therapy will be summarized. The therapy class, therapy agent and with or without concomitant chemoradiotherapy will be listed.

Concurrent and subsequent anti-cancer therapy will be summarized separately in the same way as previous anti-cancer therapy.

4.2.2.6 Radiotherapy

Number and percentage of patients had previous radiotherapy will be summarized. Other variables including site, start date, end date, etc. will be listed.

Concurrent and subsequent radiotherapy will be summarized separately in the same way as previous radiotherapy.

Number and percentage of patients receiving concurrent/ subsequent PCI will be summarized and listed. Other concurrent/ subsequent radiotherapy will be summarized in the same way as PCI. Concurrent/ subsequent PCI is the concurrent/ subsequent radiotherapy whose site or region is brain and treatment status is prophylaxis.

4.2.2.7 Use of nicotine

Nicotine use, category (never, former, current) and number of pack years used will be summarized.

4.2.3 Prior and concomitant medications

Any medications taken by the patient at any time between the date of the first dose (including the date of the first dose) of study treatment up to the date of last dose of study treatment + 90 days in the study will be considered as concomitant medication. Any medication that ended prior to the first dose of the study treatment will be considered as prior medication.

No. of patients with any prior or concomitant medications will be presented. Medications will be presented and coded using WHO Drug dictionary (WHO DD) and sorted by descending order of occurrence rate.

4.2.4 Primary endpoints

Adverse events, which start after first dose of study drug up to 90 days after the last dose of durvalumab treatment or the date of initiation of the first subsequent therapy, whichever occurs first, will be analysed in summary table. Other AEs recorded in the study will only be listed. This rule applies to all analysis of AE.

Frequency of AEs of CTCAE grade ≥ 3 , no. and percentage of patients with AEs of CTCAE grade ≥ 3 will be presented. These AEs will also be summarized by System Organ Class (SOC) and preferred term (PT). The exact 95% CIs around the incidence estimates will also be reported.

Time to event endpoints will be analysed using Kaplan-Meier method to estimate the median event time to the first AE of CTCAE grade 3 or higher. If a patient has no AE of CTCAE grade 3 or higher, the time to event will be censored at the date of DCO, death, 90 days after

the last dose of durvalumab treatment or the date of initiation of the first subsequent therapy, whichever occurs first. K-M curve will be presented.

Similar analyses will be conducted for imAEs.

An imAE is defined as an AESI that is associated with drug exposure and is consistent with an immune-mediated mechanism of action and where there is no clear alternate etiology. In general, imAEs will include AESIs that are managed using steroids, immunosuppressants and/or hormone replacement therapy.

The identification of imAEs will be made following the AstraZeneca imAE characterization charter.

1. The selection of preferred term,
2. Programmatic identification of those potential imAEs requiring medication such as steroids, immunosuppressants and/or hormone replacement therapy

All imAEs which are identified by the investigator (as recorded in CRF Adverse Events (AE)) will undergo a review by medical monitor. In addition, imAEs will be checked programmatically as described in the imAE charter on the clinical database to ensure the recording of imAEs are complete and unambiguous. If any discrepancies found, those will be resolved as an on-going basis and before DBL.

All above AEs will be listed.

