3.2.9 Incidence of AEs, SAEs, AESIs and AEs leading to treatment discontinuation

An AE is the development of an undesirable medical condition (other than progression of the malignancy under evaluation) or the deterioration of a pre-existing medical condition following or during exposure to a pharmaceutical product, whether or not considered causally related to the product. An undesirable medical condition can be symptoms (eg, nausea, chest pain), signs (eg, tachycardia, enlarged liver), or the abnormal results of an investigation (eg, laboratory findings). In clinical studies, an AE can include an undesirable medical condition occurring at any time, including run-in or washout periods, even if no study treatment has been administered.

The term AE is used to include both SAEs and non-serious AEs.

AEs will be collected from time of signing of informed consent throughout the treatment period and including the follow-up period up to 90 days after the last dose of durvalumab treatment.

An SAE is an AE occurring during any study phase (i.e. treatment, follow-up), that fulfils one or more of the following criteria:

- results in death

- is immediately life-threatening
- requires in-patient hospitalization or prolongation of existing hospitalization
- results in persistent or significant disability/incapacity
- is a congenital abnormality or birth defect
- is an important medical event that may jeopardize the patient or may require medical
- intervention to prevent one of the outcomes listed above

An AESI is one of scientific and medical interest specific to understanding of the Investigational Product and may require close monitoring and rapid communication by the investigator to the sponsor.

The AESIs reported in the AstraZeneca-sponsored durvalumab studies are defined as AEs that have a likely inflammatory or immune-mediated pathophysiological basis resulting from the mechanism of action of durvalumab and requiring more frequent monitoring and/or interventions such as corticosteroids, immunosuppressants, and/or endocrine therapy. Endocrine therapies include standard endocrine supplementation, as well as treatment of symptoms resulting from endocrine disorders (for example, therapies for hyperthyroidism include beta blockers [e.g., propranolol], calcium channel blockers [e.g., verapamil, diltiazem], methimazole, propylthiouracil, and sodium perchlorate, infusion-related reactions and hypersensitivity/anaphylactic reactions).

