4.2.6 Other safety variables

4.2.6.1 Adverse Events

The following AE summaries will be summarized similar to the primary endpoints:

- All AEs causally related to any study treatment
- All AEs by CTCAE grade
- Any CTCAE grade ≥ 3 causally related to any study treatment
- All SAEs causally related to any study treatment
- All AESIs causally related to any study treatment
- AEs leading to discontinuation of any study treatment, causally related to any study treatment
- AEs that resulted in death
- AEs that resulted in death causally related to any study treatment
- Other significant AEs

AE, AE with CTCAE grade ≥ 3 , AESI and imAE will be summarized by SOC, PT and most severe outcome. The severity of outcome is Fatal > Not Recovered/Not Resolved > Recovered/Resolved with Sequelae > Recovering/Resolving > Recovered/Resolved.

Most common AEs ($\geq 2\%$), most common AEs of CTCAE grade 3 or 4, causally related AEs, causally related AEs of CTCAE grade 3 or 4, AEs leading to interruption of durvalumab/EP/study treatment, SAEs, SAEs causally related to study treatment will also be summarized for PT and maximum CTCAE grade.

A summary of deaths will be provided with the following information:

- Total number of deaths (regardless of date and reason of deaths)
- Death related to disease under investigation only, as determined by the investigator
- Deaths related to disease under investigation, as determined by the investigator, and with an AE with outcome of death (with further subcategories for AEs with onset/worsening date prior to 90 days after the last dose of study treatment and initiation of subsequent anticancer therapy)
- AEs with outcome of death only (with further subcategories for AEs with onset/worsening date prior to 90 days after the last dose of study treatment and initiation of subsequent anticancer therapy)
- Other deaths

A list of all deaths will also be produced.

Any AE with a relatedness to study treatment of possible or probable will be considered to be causally related to study treatment for purposes of the data summaries. Relatedness should be assigned by the investigator to each study treatment individually on the eCRF. When the relatedness of an AE is missing on the eCRF, all efforts will be taken to ensure that the Investigator assigns his/her assessment of relatedness prior to database lock.

If relatedness of an AE is missing at the DBL, the AE will be considered as related to study treatment and related to durvalumab.

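### The start-date rule for AE summaries in SAP 4.2.4 has no worsening clause and an unclear first-dose-date boundary, so it can under-count grade ≥3 AEs

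*SAP*

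**What the plan says.** The controlling sentence is in SAP Section 4.2.4. It admits to the summary tables "Adverse events, which start after first dose of study drug up to 90 days after the last dose of durvalumab treatment", or up to the start of the first subsequent therapy if earlier. It continues: "Other AEs recorded in the study will only be listed. This rule applies to all analysis of AE". One sentence therefore sets the numerator for grade ≥3 AEs, imAEs, SAEs, AESIs and every other AE table.

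Other parts of the SAP bear on the lower end of that window:

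- Section 3.2.9, collection: "AEs will be collected from time of signing of informed consent throughout the treatment period". AEs with a pre-dose start will therefore be in the database.
- Section 3.2.9, definition: an AE includes "the deterioration of a pre-existing medical condition following or during exposure to a pharmaceutical product".
- Section 4.2.6.1, death summary: "with further subcategories for AEs with onset/worsening date prior to 90 days after the last dose of study treatment".
- Section 4.1.7, default: "all AEs will be considered as treatment-emergent unless the opposite can be clearly stated".
- Section 4.1.7, start dates with a missing day: "impute the 1st of the month unless month is same as month of first dose of study drug then impute first dose date". A date lacking day and month is treated the same way when the year matches, and a fully missing date generally also becomes the first-dose date.
- Table 5 (Section 4.1.6): time to first AE is the AE date minus the first-dose date, plus 1.
- Sections 3.3.9 and 4.2.3: the window for concomitant medication expressly includes the first-dose date. The AE rule has no such words.

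**The concern.** There are two weaknesses of different strength.

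The first is worsening. The rule asks only when an AE started. A screening AE of grade 1 or 2 that reaches grade ≥3 after dosing, and is kept as one record with its screening start date, fails the test and goes to a listing. Yet it is a severe event under treatment, which the grade ≥3 endpoint is meant to count.

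The second is the first-dose date. The rule does not say whether an onset on that date is in or out. A programmer working with dates could code it as strictly later than the first-dose date. That would remove Day 1 onsets and the records that 4.1.7 has just moved to that date.

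The primary objective is safety and the primary estimates are descriptive incidences. Either loss can only lower the reported toxicity.

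**Working it through.** **Step 1. Worsening, sections side by side.** Take an AE that starts between consent and first dose at grade 2 and reaches grade 3 after dosing.

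- One record with the screening start date: start is before first dose, so 4.2.4 excludes it from the grade ≥3 incidence.
- New record dated at the worsening: start is after first dose, so 4.2.4 includes it.

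The SAP does not say which way worsening is recorded, so the primary numerator depends on a convention that it does not state. The same ambiguity runs through 4.2.6.1. AEs that resulted in death are tabulated like the primary endpoints, by start date, whereas the death summary sorts by onset or worsening date. A pre-dose AE that worsens after dosing and proves fatal could appear in one and not in the other.

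**Step 2. First-dose date, sections side by side.** Take an AE with a start date, recorded or imputed, equal to the first-dose date.

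| Coding of 4.2.4 | Recorded Day 1 onset | Date imputed to Day 1 under 4.1.7 | Smallest time to first AE (Table 5) |
|---|---|---|---|
| start date > first-dose date | dropped | dropped | 1 + 1 = 2 days |
| start date ≥ first-dose date | counted | counted | 0 + 1 = 1 day |

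The first coding contradicts the treatment-emergent default in 4.1.7, since an imputed date does not clearly show a pre-dose start. It also leaves day 1 of the Table 5 count unused. The second coding agrees with both. Section 4.2.4 does not choose between them: it neither uses the term treatment-emergent nor refers to 4.1.7.

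**Step 3. The plan's precision figures.** Inputs from SAP Section 1.3: N = 300, assumed incidence 60% (grade ≥3) and 20% (imAE), exact Clopper-Pearson method. The 95% level is in 4.2.4. With x events, the lower limit is the 2.5% quantile of Beta(x, N−x+1) and the upper limit is the 97.5% quantile of Beta(x+1, N−x). Precision is half the width.

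- x = 180: 54.21% to 65.59%, half-width (65.59 − 54.21)/2 = 5.69, stated as 5.7%.
- x = 60: 15.62% to 24.98%, half-width (24.98 − 15.62)/2 = 4.68, stated as 4.7%.

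Both reproduce. The planned sample size and precision are not affected by this point.

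**Step 4. What a dropped patient costs.** Each patient whose only qualifying AE is dropped lowers the incidence by 1/300 = 0.33 points. The SAP gives no count of such patients, so k below is purely an assumption.

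| k dropped of 300 | Grade ≥3, from 60.0% (95% CI 54.2 to 65.6) | imAE, from 20.0% (15.6 to 25.0) |
|---|---|---|
| 3 | 59.0% (53.2 to 64.6) | 19.0% (14.7 to 23.9) |
| 6 | 58.0% (52.2 to 63.6) | 18.0% (13.8 to 22.8) |
| 15 | 55.0% (49.2 to 60.7) | 15.0% (11.2 to 19.6) |

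The imAE column concerns the date boundary in Step 2. Reaching grade 3 does not decide whether a patient counts for imAE incidence, which Section 3.1 defines without a grade threshold.

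**The case against.** The best defence is that the SAP compels few of these losses.

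- **Day 1 reactions.** A reader might infer that the rule excludes infusion-related or hypersensitivity reactions on Day 1. It does not say so. The text refers to the first dose, not to its date, and a reaction later that day does start after the dose. It is lost only under a strict date comparison, which the SAP does not prescribe. This objection stands: the fault is ambiguity, not exclusion.
- **Imputed dates.** A reader might infer that 4.2.4 removes what 4.1.7 imputes. The default in 4.1.7 points to inclusion, so this is an unresolved conflict between two sections. Onset time cannot settle it, because an imputed date carries no time.
- **Worsening.** Under 3.2.9 a post-dose deterioration may be entered as a new AE with its own start date, and the protocol or the eCRF instructions, not at hand, may require that. The onset/worsening wording in 4.2.6.1 also concerns the upper end of a window in a death table. This makes the loss conditional. It does not remove the gap, since a primary endpoint rule should hold under either recording practice.
- **Size.** A reader might infer a loss of several points. Nothing in the SAP supports that. A patient leaves the numerator only if no other grade ≥3 AE keeps them there. If, for illustration, 60% of patients have another such AE independently, a loss of 2 points needs 2/0.40 = 5% of all patients to have an affected grade ≥3 event, and a loss of 5 points needs 5/0.40 = 12.5%.
- **Consequence.** The primary endpoints are descriptive with no hypothesis test (4.1.3), and excluded AEs are still listed. This lowers the severity.

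**Conclusion.** The concern holds in a limited form. Followed as written, 4.2.4 leaves out of the grade ≥3 primary endpoint, and out of the other AE tables, any AE that began between consent and first dose and worsened after dosing under its existing start date. That is inconsistent with 3.2.9 and 4.2.6.1. Separately, the first-dose-date boundary is ambiguous, and one natural way of programming it contradicts 4.1.7 and Table 5.

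The direction is certain: if anything is lost, incidence is understated. The size is unknown, at 0.33 points per affected patient at N=300. The worsening limb assumes that worsened AEs keep their start date; the boundary limb assumes a strict date comparison. The SAP does not support the broader inference that every safety table is biased, or that both primary endpoints are affected by worsening to grade ≥3. Severity: should be fixed.

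**What to change.** Define a treatment-emergent AE once in the SAP: an AE with onset, or with worsening in CTCAE grade, on or after the date of first dose, other than one clearly recorded as starting before that dose and not worsening afterwards, and up to the upper limit that 4.2.4 already sets. State that partial or missing start dates follow the default in 4.1.7. Refer to this definition in 4.2.4 and in the Table 5 entry for time to first AE, using the date of worsening where worsening is what qualifies the event.

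The cost is a short definition and one flag in the ADaM specification. The reported incidence may rise slightly. Worsening can be flagged only where grade changes are captured or a new record is opened, so the SAP should say which of these the data collection provides.

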2 ANALYSIS SETS

2.1 Definition of analysis sets

2.1.1 Safety set (SS)

The safety analysis set will include all patients who received at least one dose of study treatment.

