An AstraZeneca medically qualified expert after consultation with the Global Patient Safety Physician has reviewed the AEs of interest and identified which MedDRA preferred terms contribute to each AESI. A further review will take place prior to Database lock (DBL) to ensure any further terms not already included are captured within the categories. Specific terms(PT and SOC) will be defined in an external file.

AEs leading to treatment discontinuation including AEs leading to durvalumab permanently discontinuation and AEs leading to EP permanently discontinuation.

The incidence rate of AEs/SAEs/AESIs/AEs leading to treatment discontinuation (%) = No. of patients with at least one AEs/SAEs/AESIs/AEs leading to treatment discontinuation / No. of patients in SS *100, results round to 1 decimal place.

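### SAP 4.2.4 closes the AE window by the last durvalumab dose, but the death summary in 4.2.6.1 uses the last study treatment; fatal-AE counts can disagree and some AEs during continuing EP are only listed

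*SAP*

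**What the plan says.** The primary objective (SAP 1.1) is the safety and tolerability of durvalumab plus EP. Section 4.2.4 sets the analysis window for the primary endpoints: "Adverse events, which start after first dose of study drug up to 90 days after the last dose of durvalumab treatment", cut short by the first subsequent therapy if that is earlier. It then adds "Other AEs recorded in the study will only be listed" and "This rule applies to all analysis of AE". Censoring for the time to first grade ≥3 AE, in the same section, also uses 90 days after the last durvalumab dose.

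Section 4.2.6.1 includes AEs that resulted in death among the tables to be produced in the manner of the primary endpoints, so under the 4.2.4 window. The death summary in the same section has subcategories for fatal AEs "with onset/worsening date prior to 90 days after the last dose of study treatment and initiation of subsequent anticancer therapy".

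Section 3.2.9 counts as leading to treatment discontinuation both "AEs leading to durvalumab permanently discontinuation and AEs leading to EP permanently discontinuation", so the two components are tracked separately. The same section says that AEs are collected from consent through the treatment period and on to 90 days after the last durvalumab dose.

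**The concern.** Two end points are in force for the same kind of event. If durvalumab stops before EP, a fatal AE that starts between them is in-window in the death summary and absent from the fatal-AE table of the same report. A programmer cannot follow both the general rule in 4.2.4 and the subcategory rule in 4.2.6.1.

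The durvalumab anchor can also close the window while the patient is still receiving EP. A grade ≥3 AE that starts after that point is in the database but does not enter the primary incidence. The same holds for an AE that ends EP treatment, which belongs to a secondary endpoint. The patient stays in the denominator, so any such loss lowers the reported incidence and cannot raise it.

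**Working it through.** **Inputs.** EP is given every 3 weeks for 4 to 6 cycles of 21 days (SAP Appendix A). Durvalumab is given every 3 weeks alongside EP, then every 4 weeks as monotherapy until progression (1.2). The window closes 90 days after the last durvalumab dose (4.2.4). The assumed grade ≥3 incidence is 60% with about 300 patients (1.3).

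**The plan's own figure.** The exact (Clopper-Pearson) 95% interval for 180 of 300 is 54.21% to 65.59%. The half-width is (65.59 − 54.21)/2 = 5.69, which matches the stated 5.7%. At 20% it is 4.68, matching 4.7%. All 15 cells of Table 1 reproduce. This point does not affect them.

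**Day count, on schedule.** Take the first dose as Day 1. Let d be the last cycle with durvalumab and E the last EP cycle.

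- Cycle k starts on Day 1 + 21(k − 1): Days 1, 22, 43, 64, 85, 106.
- The window closes on Day 1 + 21(d − 1) + 90 = 21d + 70.
- The last EP cycle ends 20 days after its first day, on Day 21E.
- EP-cycle days outside the window = 21E − (21d + 70) = 21(E − d) − 70, if positive.

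With E − d = 3 the result is 63 − 70 = −7, so nothing is lost. A loss needs E − d of at least 4, which leaves three patterns:

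| Last durvalumab cycle | EP cycles | Window closes | Last EP cycle ends | EP-cycle days outside |
|---|---|---|---|---|
| 1 | 5 | Day 91 | Day 105 | 14 |
| 1 | 6 | Day 91 | Day 126 | 35 |
| 2 | 6 | Day 112 | Day 126 | 14 |

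In the second pattern the whole of cycle 6 (from Day 106) is outside. Where E − d = 3, the margin is 7 days, so EP delays totalling more than 7 days would also create a loss.

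**Gap between the two 90-day limits.** The limits in 4.2.4 and 4.2.6.1 differ by the time from the last durvalumab dose to the last EP dose, 21(E − d) days. That is 21 days if durvalumab stops one cycle before EP and 105 days at most (d = 1, E = 6). The mismatch therefore covers more patterns than the loss of EP-cycle days.

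**Does continuing EP close the window as subsequent therapy?** No. Section 3.3.10 defines subsequent therapy as starting after the last dose of study drug. The durvalumab anchor alone causes the loss.

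**Size on the primary incidence.** The SAP gives neither the share of patients in these patterns (s) nor the share of those whose only grade ≥3 AE falls in the lost days (q). The ranges are assumptions: s from 1% to 10%, q from 5% to 20%. The fall in incidence is s × q:

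- Low: 0.01 × 0.05 = 0.05 points, or 0.15 of 300 patients.
- High: 0.10 × 0.20 = 2.0 points, or 6 of 300 patients.

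At the high end 180 becomes 174 of 300 (58.0%), and the half-width moves only from 5.69 to 5.73.

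**The case against.** The best defence is that the durvalumab anchor matches the data collection. AE follow-up (3.2.9) and the safety visit (1.2) are both timed from the last durvalumab dose. This stands. It rules out simply moving the window to 90 days after the last dose of any study drug: that could run past AE collection, recover nothing, and add time without ascertainment to the time-to-first-AE analysis. It does not defend dropping AEs during continuing EP, because collection runs through the treatment period.

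Second, durvalumab normally outlasts EP, so for most patients the two limits coincide. The SAP also never says outright that EP may continue once durvalumab has stopped; Section 3.2.9 only implies it by separating the two discontinuations, and the protocol would settle it. This stands too, and makes the loss of events conditional.

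Third, the death summary counts all deaths regardless of date, and AEs outside the window are still listed. So no death goes unreported; only the subcategories disagree with the fatal-AE table.

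A reader might also infer three stronger points that the SAP does not support:

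- That the primary incidence loses 0.8 to 2 points. One reaches this by supposing that 2% to 5% of 300 (6 to 15 patients) stop durvalumab early and continue EP, and that 40% of them (2.4 to 6) have their first grade ≥3 AE in the lost days. The 40% is the complement of the assumed 60% overall incidence, and every such patient is given an event. It is a ceiling on assumed rates, not an estimate.
- That the medication rule in 4.2.3, "up to the date of last dose of study treatment + 90 days", contradicts 4.2.4. It classifies medications, and a wider medication window does not conflict with an AE window.
- That the window is undefined for a safety-set member who received EP but no durvalumab. The safety set would admit such a patient, but durvalumab is given first in each cycle (Appendix A), so the case should be rare, and the point does not need it.

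**Conclusion.** The inconsistency between 4.2.4 and 4.2.6.1 is on the page and needs no assumed rate. The two limits differ by 21 to 105 days, on schedule, whenever EP outlasts durvalumab, and the SAP does not explain the difference.

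The loss of grade ≥3 AEs during EP is real but narrow. It requires that EP may continue after durvalumab stops and, on schedule, one durvalumab dose with 5 or 6 EP cycles or two doses with 6. Then 14 to 35 EP-cycle days lie outside the window. The bias is one-sided and probably small: about 0.05 to 2 points under the assumptions above, against a planned precision of 5.7 points. Sample size and precision are unaffected. This should be corrected before database lock, but it does not call the primary analysis as a whole into question.

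**What to change.** State one window in Section 4.2.4 and use it for the incidence tables, the time-to-first-AE censoring and the death-summary subcategories in 4.2.6.1. It should run from first dose to the later of (a) 90 days after the last durvalumab dose and (b) the end of the last EP cycle, or to the start of the first subsequent anti-cancer therapy if that is earlier. The existing censoring at data cut-off and death stays as it is.

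Use 90 days after the last dose of any study treatment only if it is confirmed that AE collection under Section 3.2.9 runs that long.

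The cost is SAP wording and one derivation flag. The reported grade ≥3 incidence may come out slightly less favourable.
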